10.4.6 Pharmacokinetic assessments

Blood samples for PK assessments must be collected at the time points specified in the schedule of procedures (Section 4).

Collection, handling and shipment instructions for PK blood samples are provided in a laboratory manual.

Serum samples for determination of tralokinumab concentrations will be analysed by a laboratory using a validated bioanalytical method. Details of the analytical method used will be described in the bioanalytical report.

Samples will be retained for as long as the quality of the material permits evaluation but for no longer than 12 months after completion of the clinical trial report (CTR).

10.4.7 Anti-drug antibodies measurements

Blood samples will be collected for determination of anti-tralokinumab antibody levels at pre-determined time points according to the schedule of procedures (Section 4).

Collection, handling and shipment instructions for ADA blood samples are provided in a separate laboratory manual.

Trial ID: LP0162-1339	Date: 29-Aug-2018	Version: 4.0
		Page 76 of 129

Serum samples for determination of presence or absence of ADA will be analysed by a laboratory using a validated bioanalytical method. A tiered testing scheme will be employed, with the first step being screening. Samples found positive in the screening step will be tested in the confirmatory step. Samples confirmed positive for ADA in the confirmatory step will undergo endpoint titre determination and will be analysed for the presence of neutralising antibodies (nAB). Details of the analytical method used will be described in the ADA bioanalytical report.

Samples will be retained for as long as the quality of the material permits evaluation but for no longer than 15 years after marketing authorisation.

10.5 Estimate of total blood volume collected

Blood samples will be drawn for safety (chemistry, haematology, and serology), PK, and ADAs. The total volume of blood to be withdrawn is approximately 180 mL which is less than the volume of blood drawn during a blood donation (approximately 500 mL).

11Adverse events

AEs and SAEs are defined in Appendix 1: Definitions of adverse events and serious adverse events.

Classification of AEs in terms of severity, causality and outcome are defined in Appendix 2: Classification of adverse events.

11.1 Collection of adverse events

AEs must be collected from time of first trial-related activity after the subject has signed the informed consent form (ICF) until completion of the clinical trial (defined as the safety follow-up visit 16 weeks after last injection of IMP). For subjects entering the long-term extension trial (LP0162-1337, ECZTEND), any (S)AE with onset before the final visit in LP0162-1339 should be reported in LP0162-1339. If ongoing, the (S)AE will also be recorded as medical history in ECZTEND.

AEs must be assessed by medically qualified personnel.

At all visits, the subject will be asked a non-leading question by the investigator about AEs, for example: "How have you felt since I saw you last?" No specific symptoms should be asked for. It is important that the investigator also observes the subject for any changes not reported by the subject and records these changes.

Trial ID: LP0162-1339	Date: 29-Aug-2018	Version: 4.0
		Page 77 of 129

Clinically significant abnormal findings related to vital signs, physical examination, ECGs, or laboratory tests after the first screening visit must be reported as an AE in accordance with Section 11.2; also see Sections 10.4.1 (vital signs), 10.4.2 (physical examination), 10.4.3 (ECGs), and 10.4.5 (laboratory tests) for further details.

11.2 Reporting of adverse events

AEs reported by the subject or observed by the investigator must be recorded on the AE form of the eCRF and should be described in the following manner:

The *AE term* must be in precise English medical terminology (i.e. not necessarily the exact words used by the subject). Whenever possible, a specific diagnosis should be stated (for example 'allergic contact dermatitis').

The *duration* of the AE must be reported by the start date and stop date of the event. In addition, it must be recorded whether the AE started prior to start of IMP.

AEs must be classified in terms of severity, causality and outcome according to the definitions in Appendix 2: Classification of adverse events.

Action taken with trial treatment: Any action taken with IMP or NIMP (TCS) as a consequence of the AE must be recorded (dose not changed, dose reduced, dose increased, drug interrupted, drug withdrawn, not applicable, unknown).

Other action taken: any other action taken as a result of the AE must be recorded (none, concomitant medication, concomitant procedure).

Withdrawn due to AE: it must be recorded whether the AE leads to withdrawal from the trial.

11.3 Reporting of serious adverse events

The criteria that define an AE as serious (i.e., an SAE) are defined in Appendix 1: Definitions of adverse events and serious adverse events.

11.3.1 Investigator reporting responsibilities

Any SAE must be reported to LEO on the (paper) SAE Form within 24 hours of first knowledge. This report should contain an assessment of available information on seriousness, severity, causal relationship to the IMP or IMP device, causal relationship to NIMP, comparator or trial procedure, the action taken, the outcome to date, and a narrative description of the course of the event.

Trial ID: LP0162-1339	Date: 29-Aug-2018	Version: 4.0
		Page 78 of 129

The completed SAE form must be faxed or scanned and e-mailed to Global Pharmacovigilance, LEO using the e-mail address or fax number below:

Global Pharmacovigilance, LEO

E-mail address: [contact]

[contact]

It may be relevant for the investigator to enclose other information with the SAE form, such as anonymised reports of diagnostic procedures, hospital records, autopsy reports, etc.

Additionally, Global Pharmacovigilance, LEO may request further information in order to fully assess the SAE. The investigator must forward such information to LEO upon request by fax or e-mail (see contact details above).

The investigator must notify the local institutional review board(s) (IRB[s])/ independent ethics committee(s) (IEC[s]) of SAEs as required by current applicable legislation for the concerned country.

SAEs occurring after the completion of the clinical trial (i.e., after the safety follow-up visit at Week 46) should not be routinely sought or collected. However, such events should be reported to LEO (see contact details above) if the investigator becomes aware of them.

11.3.2 LEO reporting responsibilities

Global Pharmacovigilance, LEO is responsible for assessing whether or not an SAE is expected. The relevant reference document for this clinical trial is:

For the IMP, the Investigator's Brochure, edition 16 and subsequent updates must be used.

For the NIMP (mometasone furoate, 0.1% cream) the latest version of the approved label must be used.

Global Pharmacovigilance, LEO will notify the regulatory authorities and concerned investigators of SAEs according to the current applicable legislation for the concerned countries.

The IRB(s)/IEC(s) will be notified of SAEs according to the current applicable legislation for the concerned countries.

Trial ID: LP0162-1339	Date: 29-Aug-2018	Version: 4.0
		Page 79 of 129

For all countries except the US, all SAEs which are assessed as causally related to the IMP(s) by either the investigator or LEO (ICH E2A Guideline), and which are unexpected (Suspected, Unexpected Serious Adverse Reactions [SUSARs]), are subject to expedited reporting to regulatory authorities and IRB(s)/IEC(s) according to the current applicable legislation in the concerned countries. Investigators will be notified of such SUSARs and the evolving safety profile on an ongoing basis.

For the US, as per Guidance for Industry and Investigators - Safety Reporting Requirements for INDs and BA/BE Studies, only those events for which the sponsor determines there is a reasonable possibility of a causal relationship are subject to IND Safety Reporting. Investigators will be notified of the evolving safety profile on an ongoing basis.

11.4 Other events that require expedited reporting

11.4.1 Pregnancy

Any pregnancy occurring during the clinical trial must be reported to LEO within 24 hours of first knowledge using the (paper) Pregnancy Follow Up Form (Part I). All such pregnancies must be followed up until delivery or termination and final outcome must be reported on the (paper) Pregnancy Follow Up Form (Part II) within 24 hours of first knowledge.

The completed Pregnancy Follow Up Forms must be faxed or scanned and e-mailed to Global Pharmacovigilance, LEO. Contact details are given in Section 11.3.1.

Pregnant subjects must permanently discontinue IMP (see Section 9.7.1).

11.5 Reporting of other events

11.5.1 Adverse events of special interest

The events listed in Panel 10 are considered adverse events of special interest (AESIs) in this trial and will require that the investigator provides additional information to LEO. An AESI may be serious (requiring expedited reporting, Section 11.3) or non-serious.

Trial ID: LP0162-1339	Date: 29-Aug-2018	Version: 4.0
		Page 80 of 129

Panel 10 Adverse events of special interest

Adverse event of special interest	Additional information to be provided (if available ¹)		
	Skin findings:		
	Lesion type.		
	Disseminated / localised.		
Eczema herpeticum	• Location.		
Dezema nei peticum	Present in an area with visible eczema / no visible		
	eczema / present in areas with and without eczema.		
	Monomorphic / polymorphic.		
	Confirmation of herpes simplex virus.		
Malignancies diagnosed after	Histology report.		
randomisation, excluding basal	Oncology assessment.		
cell carcinoma, localised squamous	• Treatments (surgery, radiation, chemotherapy, other).		
cell carcinoma of the skin, and carcinoma in situ of the cervix			
	Skin swab		
Skin infections requiring systemic treatment	Outcome.		
treatment			
	Aetiology (viral, bacterial, allergic, unknown).		
Conjunctivitis	 Bacterial culture outcome (for events with bacterial aetiology). 		
	 Diagnosis confirmed by ophthalmologist. 		
	 Aetiology (infectious, non-infectious, other, unknown). 		
Keratoconjunctivitis	Bacterial culture outcome (for events with bacterial		
2201 utocon guncer (1225	aetiology).		
	Diagnosis confirmed by ophthalmologist.		
	Aetiology (infectious, non-infectious, other,		
	unknown).		
	Bacterial culture outcome (for events with bacterial		
Keratitis	aetiology).		
	Diagnosis of herpes simplex keratitis (for events with		
	viral aetiology).		
	 Diagnosis confirmed by ophthalmologist. 		

¹The additional data to be recorded in the eCRF are not a requirement, but are to be reported by the investigator, if available, for example as part of standard clinical practice.

Trial ID: LP0162-1339	Date: 29-Aug-2018	Version: 4.0
		Page 81 of 129

11.5.2 Overdose

An overdose is defined as a subject receiving a dose of IMP in excess of that specified in this protocol.

The term overdose must be documented on the AE form of the eCRF. In addition, AEs originating from overdose must be documented on a separate line.

LEO does not recommend specific treatment for an overdose. The investigator will use clinical judgment to treat any overdose if necessary.

11.5.3 Medication error

Medication error refers to any unintentional error in the dispensing or administration of an IMP while in the control of the investigator or subject. Broadly, medication errors fall into four categories: wrong medication, wrong dose (including strength, form, concentration, amount), wrong route of administration, or wrong subject.

The medication error must be documented on the AE form in the eCRF. In addition, AEs originating from a medication error must be documented on a separate line specifying the category of error (see definitions above).

If the medication error is due to device malfunction, such malfunction must be reported as a device complaint as described in Section 9.10.

11.5.4 Misuse

Misuse refers to situations where the IMP is intentionally and inappropriately used not in accordance with the protocol.

The term misuse must be documented on the AE form in the eCRF. In addition, AEs originating from misuse must be documented on a separate line.

11.5.5 Abuse

Abuse relates to the sporadic or persistent, intentional excessive use of an IMP which is accompanied by harmful physical or psychological effects.

The term abuse must be documented on the AE form in the eCRF. In addition, AEs originating from abuse must be documented on a separate line.

Trial ID: LP0162-1339	Date: 29-Aug-2018	Version: 4.0
		Page 82 of 129

11.5.6 Aggravation of condition

Any clinically significant aggravation/exacerbation/worsening of any medical condition(s), compared to screening, must be reported as an AE.

11.6 Follow-up for final outcome of adverse events

During the trial, the investigator should follow up for final outcome on all AEs (including SAEs). Once a subject leaves the clinical trial, the investigator should follow up on the outcome of all non-serious AEs classified as of possible/probable relationship to the IMP for 2 weeks or until the final outcome is determined, whichever comes first. SAEs must be followed up until a final outcome has been established, i.e. the follow-up may continue beyond the end of the clinical trial. For SAEs, which have stabilised and cannot be expected to recover during trial or safety follow-up periods, for example chronic illnesses, the final outcome should be considered recovered and a statement that the SAE has stabilised should be added to the narrative in the SAE form.

11.7 Handling of an urgent safety measure

An urgent safety measure is a measure taken to implement an action/protocol deviation under an emergency. This is defined within the EU Directive as "...the occurrence of any new event relating to the conduct of the trial or the development of the investigational medicinal product where that new event is likely to affect the safety of the subjects, the sponsor and the investigator shall take appropriate urgent safety measures to protect the subjects against any immediate hazard." (34).

If the investigator becomes aware of information that necessitates an immediate change in the clinical trial procedure or a temporary halt to the clinical trial in order to protect clinical trial subjects from any immediate hazard to their health and safety, the investigator can do so without prior approval from LEO, regulatory authority(ies), or IRB(s)/IEC(s).

The investigator must immediately inform LEO - by contacting the clinical project manager or medical expert - of this change in the clinical trial procedure or of the temporary halt providing full details of the information and the decision-making process leading to the implementation of the urgent safety measure.

LEO must act immediately upon receipt of the urgent safety measure notification in accordance with internal procedures and local legislation.

Trial ID: LP0162-1339	Date: 29-Aug-2018	Version: 4.0
		Page 83 of 129

12 Statistical methods

12.1 Sample size

A total of 369 subjects will be randomised 2:1 to initial treatment in this trial (246 subjects in the tralokinumab+TCS arm; 123 subjects in the placebo+TCS arm).

The primary endpoints for initial treatment, IGA 0/1 and EASI75 at Week 16, are to be evaluated hierarchically testing both hypotheses of no difference between active and placebo at the 5% significance level. The hypothesis for IGA 0/1 will be tested first; if significant, the EASI75 hypothesis will be tested.

The null hypothesis for the first primary endpoint is that there is no difference at Week 16 in obtaining IGA 0/1 between tralokinumab+TCS and placebo+TCS. The null hypothesis for the second primary endpoint is that there is no difference at Week 16 in obtaining EASI75 between tralokinumab+TCS and placebo+TCS. Each hypothesis will be tested against the 2-sided alternative that there is a difference between the 2 treatment groups.

For the single endpoint IGA 0/1 at Week 16, a sample size of 369 subjects randomised 2:1 will provide 90% power to detect a difference between the 2 arms, assuming response rates of 30% for tralokinumab+TCS and 15% for placebo+TCS. For the single endpoint EASI75 at Week 16, a sample size of 369 will provide a nominal power >99.9% to detect a difference between tralokinumab+TCS and placebo+TCS, assuming EASI75 response rates of 40% and 15%, respectively. The combined power for demonstrating a significant difference for both endpoints is therefore effectively also 90% with a sample size of 369 subjects, even when assuming no correlation between the 2 primary endpoints. In all cases, the evaluations will be made with a 2-sided 5% significance level.

12.2 Trial analysis sets

All screened subjects will be accounted for in the CTR.

All subjects randomised to initial treatment are included in the full analysis set and will be analysed for efficacy up to Week 16. Exclusions from the full analysis set can be considered in special cases as described in ICH E9, Section 5.2.1, Full Analysis Set. If it is decided to exclude a randomised subject from the full analysis set, a justification addressing ICH E9 will be given.

A per protocol analysis set will be used as an efficacy subset for the analysis of the primary endpoints up to Week 16, and analyses based on the per protocol analysis set will be

Trial ID: LP0162-1339	Date: 29-Aug-2018	Version: 4.0
		Page 84 of 129

performed to support the results obtained for the full analysis set. The per protocol analysis set will be defined by excluding subjects from the full analysis set for whom any of the following conditions apply:

- receive no treatment with the IMP.
- provide no assessment of IGA or EASI following start of treatment.
- are known to have taken the wrong IMP throughout the initial treatment period of the trial.
- do not fulfil the inclusion criteria no. 3, 6, 7, and 8.

A safety analysis set will be defined by excluding subjects from the full analysis set who either received no treatment with IMP and/or for whom no post-baseline safety data are available.

A continuation treatment analysis set will be defined as subjects in the full analysis set who have not withdrawn from trial prior to or at the Week 16 visit (visit 11).

A continuation treatment safety analysis set will be defined as subjects who are exposed to IMP at or after the Week 16 visit (visit 11).

Based on the above-mentioned rules, the inclusion/exclusion of subjects from the trial analysis sets will be documented in the statistical analysis plan update before breaking the randomisation code.

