12.3.3 Exposure and treatment compliance

12.3.3.1 Exposure

Exposure to treatment will be presented for the safety analysis set (initial treatment) and continuation treatment safety analysis set (continuation treatment) as days of exposure per treatment group.

For the full trial period, the days of exposure on tralokinumab irrespective of treatment group will be summarised - subtracting potential periods on placebo - for the safety analysis set.

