12.3.3.2 Treatment compliance

Adherence to treatment regimen will be recorded in the eCRF. The log of drug administration may be used as source. If any complications or deviations in administration are observed, these will be described as protocol deviations.

Adherence will be presented for the safety analysis set (initial treatment) and for the continuation treatment safety analysis set (continuation treatment) for each treatment group.

[figure not shown]

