12.3.9 Analysis of safety

The analyses of safety will be based on the safety analysis set. The reporting of safety data will be presented separately for initial treatment and continuation treatment.

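### The safety analysis set is nested in the full analysis set, so a dosed subject excluded from the full analysis set also leaves the initial-period safety tables

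*Protocol*

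**What the plan says.** Protocol section 12.2 sets up the analysis sets in a chain.

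- Full analysis set: "All subjects randomised to initial treatment are included in the full analysis set", for the analysis of efficacy up to Week 16. Then: "Exclusions from the full analysis set can be considered in special cases as described in ICH E9", with a justification for each exclusion.
- Safety analysis set: formed by "excluding subjects from the full analysis set who either received no treatment with IMP and/or for whom no post-baseline safety data are available".
- Continuation treatment safety analysis set: "subjects who are exposed to IMP at or after the Week 16 visit". It has no parent set and no condition on available data.

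Section 12.3.9 then states: "The analyses of safety will be based on the safety analysis set". Initial-period exposure (12.3.3.1), adherence (12.3.3.2), vital signs (12.3.9.2) and laboratory data (12.3.9.3) are tied to the same set. So is the full-trial summary of days on tralokinumab (12.3.3.1). Section 12.2 has no clause that keeps a dosed subject in the safety set after exclusion from the full analysis set.

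**The concern.** Safety tables should describe everyone who was exposed. Here membership depends first on a decision about an efficacy set. If a dosed subject is excluded from the full analysis set, the safety denominator loses that exposure and the numerator loses any event that was observed. AE and SAE frequency is an additional secondary endpoint (Panel 4), and section 12.3.9.1 compares the percentage of subjects with AEs between arms in the initial period. The affected figures are therefore reported results.

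The protocol is also not consistent with itself. Its other safety set, in the same section, uses exposure alone. A subject excluded from the full analysis set but dosed at Week 16 would belong to the continuation safety set, but not to the safety analysis set or the full-trial exposure summary.

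**Working it through.** The protocol states no figure for the safety set, so there is none to reproduce. The check is on the logic of the definitions, followed by simple arithmetic on the planned arm sizes in section 12.1 (246 and 123, together 369).

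**1. Who can be dosed and still be outside the set.** Let F be the full analysis set, D the dosed subjects and P the subjects with post-baseline safety data. Section 12.2 gives

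safety set = F ∩ D ∩ P.

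A dosed subject is therefore missing in either of two cases:

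- (a) not in F;
- (b) in F but not in P. The wording joins the two exclusion criteria by and/or, so either one is enough.

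**2. What each case removes.**

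- Case (a) can remove an observed event together with the subject.
- Case (b) cannot, provided a recorded post-dose event counts as post-baseline safety data. The subject then has no recorded event, and only the denominator changes.

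**3. How often case (b) could arise.** Section 9.1.3.1 requires at least 30 minutes of monitoring after the Week 0 dose, with vital signs entered in the eCRF. Section 8.5 requires a record of whether any safety evaluation followed exposure when no post-baseline visit was attended. If these Day 0 data count, almost every dosed subject is in P. However, section 7.1 calls Day 0 baseline, section 9.1.3.1 makes it the first dosing day, and the protocol does not say whether same-day post-dose data are post-baseline.

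**4. Size of case (a).** With x events among n subjects, removing one subject with an event changes the percentage from x/n to (x − 1)/(n − 1). For infrequent events the drop is close to 1/n:

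- tralokinumab: 1/246 = 0.41 points;
- placebo: 1/123 = 0.81 points.

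Illustration with an assumed count of 5 subjects with SAEs on tralokinumab: 5/246 = 2.0% becomes 4/245 = 1.6% with one such subject removed, and 2/243 = 0.8% with three removed.

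**5. Size of case (b).** Removing k event-free subjects changes x/n to x/(n − k). With an assumed AE percentage of 60%:

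| Arm | k = 0 | k = 1 | k = 5 |
|---|---|---|---|
| Tralokinumab (147.6 expected subjects with AEs) | 60.0% (n = 246) | 147.6/245 = 60.2% | 147.6/241 = 61.2% |
| Placebo (73.8 expected subjects with AEs) | 60.0% (n = 123) | 73.8/122 = 60.5% | 73.8/118 = 62.5% |

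The event counts, the 60% and the values of k are assumptions. The protocol gives no SAE or AE percentages for this trial and no expected number of exclusions.

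**The case against.** The best defence is that the rule will seldom apply. Inclusion of all randomised subjects is the default. An exclusion needs a special case and a justification, and section 12.2 has set membership documented before the randomisation code is broken. All of this stands. It limits both the number of subjects and the scope for bias, but a justified, blinded exclusion would still remove a dosed subject from the safety tables.

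Three stronger readings are tempting, and the protocol does not support them.

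- **Events would disappear from the report.** Section 12.3.9.1 puts all recorded AEs in the subject listings and requires a narrative for each SAE. Section 12.3.1 gives disposition for all randomised subjects. The loss is from tables and percentages.
- **Any dosed subject lost before the first post-baseline visit is dropped.** The criterion is absence of safety data, which is not the same as absence of a visit, and section 8.5 treats the two separately. Step 3 shows why the data criterion should rarely apply.
- **Failing eligibility or lacking IGA or EASI data removes a subject from the safety set.** Section 12.2 lists those reasons for the per protocol set, which does not feed the safety set. For the full analysis set it lists no reasons and refers to ICH E9.

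The mismatch with the continuation set is also narrow in practice. A subject who reaches Week 16 in the normal course has had many safety assessments, so only exclusion from the full analysis set could put that subject in one safety set and not the other.

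**Conclusion.** The point holds as a defect in a stated definition. It is small. Dependence on the full analysis set is the part that matters, because it can take an observed event out of the initial-period safety tables and exposure out of the full-trial tralokinumab summary. The data-availability condition is secondary: it can only raise AE percentages slightly, and it leaves open whether Day 0 post-dose data count.

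The size is about 0.4 points per affected subject with an event on tralokinumab and 0.8 on placebo. This assumes that all planned subjects are dosed and that the event is infrequent. The number of affected subjects is unknown and likely to be very few. No sample size, power or significance level changes.

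**What to change.** In section 12.2, or in the statistical analysis plan update that the protocol foresees before the code is broken, define the safety analysis set as all randomised subjects who received at least one dose of IMP, independently of the full analysis set. Remove the condition on post-baseline safety data. Instead, report by arm the number of dosed subjects without any post-dose safety data, for example in the disposition table. The rule then matches that of the continuation treatment safety analysis set, and the Day 0 question no longer affects membership.

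The cost is one sentence and one line in a table. The downside is that AE percentages may fall marginally when subjects without data enter the denominator. Reporting their number lets a reader judge the effect.
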